## 5.2 PD ENDPOINTS

All PD parameters are obtained from the smoothed PD data reported as mg-glucose/kg/min.

### 5.2.1 Primary Endpoints

- (1)  $GIR_{max}$ , in units of mg-glucose/kg/min, is defined as the maximum of infusion rate of glucose administrated intravenously needed to maintain target blood glucose level:

$$GIR_{max} = \max(GIR_1, \dots, GIR_i, \dots, GIR_n) \quad i = 1, 2, 3 \dots n \quad (24)$$

where  $n=720$  is the number of GIR recorded for a given treatment of a given subject.

- (2)  $AUC_{GIR(0-12h)}$ , in units of mg-glucose/kg, can be calculated per the trapezoidal rule as given the Eq. (25):

$$AUC_{GIR(0-12h)} = \sum_{i=1}^{n-1} \frac{GIR_i + GIR_{i+1}}{2} (t_{i+1} - t_i) \quad (25)$$

where  $n$  is the number of available PD measurements,  
 $t_1=0$ , and  $t_n = 720$  minutes (12 hours).

### 5.2.2 Secondary Endpoints

- (1)  $tGIR_{max}$ , defined as time until maximum glucose infusion rate is reached is an observed value, corresponding when  $GIR_{max}$  appears, and is represented in units of “minutes”, or “min”.
- (2) Partial  $AUC_{GIR(t_{v1}-t_{v2})}$ , in units of mg/kg, can be calculated per the trapezoidal rule and sampling time for each treatment of each subject similarly as the Eq. (14):

$$AUC_{GIR(t_{v1}-t_{v2})} = \sum_{j=v_1}^{v_2-1} \frac{GIR_j + GIR_{j+1}}{2} (t_{j+1} - t_j) \quad (26)$$

where,  $t_{v1}$  and  $t_{v2}$  are the starting and ending times of the partial  $AUC_{GIR(t_{v1}-t_{v2})}$ , respectively;

The following partial AUC of GIR will be calculated:

- $AUC_{GIR(0-last)}$ ,

- $AUC_{GIR(0-1h)}$ ,
- $AUC_{GIR(0-2h)}$ ,
- $AUC_{GIR(0-4h)}$ ,
- $AUC_{GIR(4-12h)}$ .

- (3)  $tGIR_{onset}$ , in units of “minutes”, or “min”, defined as time of start of GIR post-dose, is read as the earliest time from the smoothed PD curve when  $GIR > 0$ .
- (4)  $tGIR_{last}$ , in units of min, is read from the smoothed PD curve as the latest time when  $GIR > 0$ .
- (5)  $GIR_{last}$ , in units of %/min, defined as the value of last measurable GIR from smoothed PD curve.
- (6)  $tGIR_{50\%E}$ , defined as the time reaching 50% maximal GIR before  $tGIR_{max}$ , is obtained from the smoothed PD curve per interpolative rule.

$$tGIR_{50\%E} = \frac{\left(\frac{1}{2} GIR_{max} - GIR_j\right)(t_j - t_{j+1})}{GIR_j - GIR_{j+1}} - t_j \quad (27)$$

where  $t_j$  and  $t_{j+1}$  are time point corresponding to  $GIR_j$  and  $GIR_{j+1}$ , the two adjacent data points on smoothed GIR-time curve;

$$GIR_j \leq \frac{1}{2} GIR_{max} \text{ and } GIR_{j+1} > \frac{1}{2} GIR_{max} ;$$

$$t_j < tGIR_{max} .$$

- (7)  $tGIR_{50\%L}$ , defined as the time reaching to 50% maximal GIR after  $tGIR_{max}$ , is obtained from the smoothed PD curve per interpolative rule.

$$tGIR_{50\%L} = \frac{\left(\frac{1}{2} GIR_{max} - GIR_j\right)(t_j - t_{j+1})}{GIR_j - GIR_{j+1}} - t_j \quad (28)$$

$$\text{where } GIR_j \geq \frac{1}{2} GIR_{max} \text{ and } GIR_{j+1} < \frac{1}{2} GIR_{max} , t_j \geq tGIR_{max} .$$

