#### 4.3.1 Precision of Clamp Data

The precision is reported as CV (coefficient of variance) of device blood sugar. For a given subject  $i$  in a given treatment  $X$  ( $X=T$  or  $R$ ) at a given time point  $t$ , the blood glucose (BG) level is denoted as  $g_{i,X}(t)$ , and the average of BG is obtained as

$$G_{i,X} = \frac{1}{n_t} \sum_t g_{i,X}(t) \quad (5)$$

Calculations for CV by Eq. (5) is based on each clamp from the minute that the glucose infusion rate is initiated (Start of GIRa) to the minute that the glucose infusion rate is no longer required (End of GIRb) or at the end of the clamp at the 12-hour mark, whichever appears first. Note that an End of GIR is not necessarily an end of the clamp. In Eq. (5),  $n_t$  is total number of GIR data for the subject in the treatment per the above calculation method.

The precision for the clamp data point, denoted as  $p_{i,X}$ , can be measured using the coefficient of variance (CV, in %) as defined below:

$$p_{i,X} = \frac{\sigma_{i,X}}{G_{i,X}} \times 100\% \quad (6)$$

where  $\sigma_{i,X}$  is the standard deviation of the BG data of  $g_{i,X}(t)$ . It is expected that  $p_{i,X} < 12\%$ .

For the subjects with clamp precision  $\geq 10\%$ , the data should be flagged and tabulated. If  $p_{i,X} \geq 12\%$ , the clamp data for the treatment of the subject should be rejected.

The clamp precision for a given treatment  $X$ , is then calculated as

---

a **Start of GIR:** After dosing of Insulin Aspart, the onset of insulin action was identified by a decline of 5mg/dL or more for glucose concentration from the baseline level, the corresponding onset time is denoted as  $t_{\text{onset}}$ . At or after  $t_{\text{onset}}$ , the first time point with  $\text{GIR}(t) > 0$ , is the start of GIR.

b **End of GIR:** If the last time point with  $\text{GIR}(t_{\text{last}}) > 0$ , then starting from  $t = t_{\text{last}} + 1$ , the glucose infusion rate is no longer required, the time for end of GIR is  $\text{Min}(t_{\text{last}} + 1, 720)$ .

$$P_X = \frac{1}{n_X} \sum_{i=1}^{n_X} p_{i,X} \quad (7)$$

where  $n_X$  is the number of subjects in the treatment X.

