#### 4.4 SMOOTHING OF PD DATA

During the 12-hour study, GIR PD data were collected every minute for each treatment (T or R) of each subject using clamp technique. In fact, 721 PD data points (0-720 min) were measured for each treatment (T or R) of each subject.

Due to the nature of the clamp technique, the PD data are highly fluctuating as a function of time, so smoothing is required before calculating PD parameters (such as  $GIR_{max}$ ,  $AUC_{GIR}$ , etc.). The smoothing procedure has been designed to accommodate data for which

$$y_i = k(t_i) + \varepsilon_i \quad (11)$$

where  $y_i$  is the actual PD observation as GIR at time  $i$ ,  $k$  is a smooth function of PD, and the  $\varepsilon_i$  are random variables with mean 0 and constant scale,  $\varepsilon_i \in (0, \sigma^2)$ . Within such a framework,  $\hat{y}_i$  is an estimate of  $k(t_i)$ . The assumption of smoothness allows points in a neighborhood of  $(t_i, y_i)$  to be used to form  $\hat{y}_i$ .

For the actual smoothing, the SAS standard program Locally Estimated Scatterplot Smoothing (LOESS) in SAS/STAT 13.1 is used.

The LOESS method uses weighted least squares to fit linear or quadratic functions of the predictors to the centers of the neighborhoods. The radius of each neighborhood is chosen so that the neighborhood contains a specified percentage of the data points. The fraction of the data, called the smoothing parameter, in each local neighborhood controls the smoothness of the estimated surface. Data points in a given local neighborhood are weighted by a smooth decreasing function of their distance from the center of the neighborhood. Therefore,

$$M = s N \quad (12)$$

where, N is the total number of experimental data points. For PD data of this study, N=721.

M is the number of data points in a given local neighborhood, and  
s is the smoothing parameter, specifying a fraction of the total PD data.

This SAP suggests using smoothing parameter  $s=0.0125$ , so that M=9, namely there are 9 data points in each neighborhood.

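### SAP 5.2.2 reads the start, end and last value of GIR from the smoothed curve as the points where it exceeds zero; the timing error is minor, but GIRlast is a small fraction of the real last rate unless infusion runs to 12 h

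*SAP*

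**What the plan says.** SAP 5.2 sets the general rule: "All PD parameters are obtained from the smoothed PD data reported as mg-glucose/kg/min". SAP 5.2.2 applies it to three secondary endpoints:

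- item (3): tGIRonset "is read as the earliest time from the smoothed PD curve when" GIR is above zero;
- item (4): tGIRlast "is read from the smoothed PD curve as the latest time when" GIR is above zero;
- item (5): GIRlast is "defined as the value of last measurable GIR from smoothed PD curve".

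The SAP sets no minimum for a measurable GIR, and no step puts back the zeros on record before and after the infusion.

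SAP 4.4 describes the smoother. It suggests a smoothing parameter of 0.0125, "namely there are 9 data points in each neighborhood". It does not choose between linear and quadratic local fits, and it does not name the weight function.

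SAP 4.3.1 has its own start and end of GIR, used as the averaging window for clamp CV and DFT. Under footnote a, the start is the first minute with GIR above zero at or after a glucose fall of at least 5 mg/dL. Footnote b says that from the minute after t_last "the glucose infusion rate is no longer required, the time for end of GIR is" Min(t_last + 1, 720). Neither footnote mentions smoothing.

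Protocol 2.4 states smoothing only for Gmax and the AUC of GIR.

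**The concern.** A local fit spreads each positive minute into the zero minutes beside it. A rule of the form above-zero, applied after smoothing, therefore finds the edge of the smoother and not the edge of the infusion. The start can be read too early and the end too late. The value at that late end is a remnant of the smoothing weights, not a rate that was infused.

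This matters most for GIRlast. If infusion stops early, the smoothed curve has a tail and GIRlast is read from it. If infusion is still running at 720 min there is no tail, and GIRlast is the actual rate. One endpoint then measures two different things, depending on when infusion stopped. SAP 6.4.2.2 analyses secondary endpoints in the same way as the primary ones, that is, as a T/R ratio on the log scale, where a very small artificial value carries great weight.

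**Working it through.** **Inputs.** From SAP 4.4: "For PD data of this study, N=721" (one value per minute, 0-720), s = 0.0125 and M = 9. On degree, 4.4 says only that the method "uses weighted least squares to fit linear or quadratic functions of the predictors", so both were run. Assumed: tricube weights, and the GIR profiles, because the documents contain no GIR data.

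**The plan's own figure.** M = s x N = 0.0125 x 721 = 9.0125, hence 9 points. This reproduces.

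**Weights.** Nine points centred on a minute reach 4 min each way. Tricube weight at distance d is (1 - (d/4)^3)^3: 1 at d = 0, 0.954 at 1, 0.670 at 2, 0.193 at 3 and 0 at 4. The sum is 1 + 2 x (0.954 + 0.670 + 0.193) = 4.63. The smoother thus reaches 3 min to each side.

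**Local linear fit, away from the ends of the clamp.** The fit is a weighted mean with weights 0.0417, 0.1446, 0.2058, 0.2158, 0.2058, 0.1446, 0.0417. Three minutes after the last positive minute, the curve equals 0.193/4.63 = 0.0417 times the last recorded rate; at four minutes it is zero. So tGIRlast is 3 min late, tGIRonset is 3 min early by symmetry, and GIRlast is 4.2% of the real last rate. In 2,000 simulated noisy profiles all three held every time.

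**Local quadratic fit.** The weights are -0.059, 0.0567, 0.3039, 0.3966, 0.3039, 0.0567, -0.059. One minute after a constant infusion stops, the curve is 0.3039 + 0.0567 - 0.059 = 0.30 of the rate. At two minutes it is 0.0567 - 0.059, which is below zero. So tGIRlast is 1 min late and GIRlast is 30%. In noisy profiles, onset was 1-2 min early in 1,936 of 2,000 and last time 1-2 min late in 1,980 of 2,000. The GIRlast fraction had a median of 0.11 (5th to 95th percentile 0.005 to 0.40), so 30% is not a general figure.

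**Examples (rates in mg/kg/min, times in min).**

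| Assumed profile | Quantity | Recorded | Linear | Quadratic |
|---|---|---|---|---|
| Tapering, 30 to 540 | onset | 30 | 27 | 29 |
| | last time | 540 | 543 | 541 |
| | GIRlast | 1.09 | 0.0455 | 0.329 |
| Constant 0.5, stops at 600 or 700 | GIRlast | 0.50 | 0.021 | 0.151 |
| Constant 0.5, runs to 720 | GIRlast | 0.50 | 0.50 | 0.50 |

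**Stops close to 12 h.** For a constant rate stopping at 713-719 min, the fits at the end of the grid make the linear GIRlast fraction erratic, from 0.002 to 0.48.

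**Effect on T/R.**

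- Both clamps stop by about 712 min, linear fit: 0.0417 appears in numerator and denominator and cancels.
- Both stop early, quadratic fit: the fraction varies from clamp to clamp, so it need not cancel.
- One clamp stops early and the other runs to 720 min, equal true last rates of 0.5: 0.50/0.021 = about 24 (linear) or 0.50/0.151 = about 3.3 (quadratic), where the true ratio is 1.

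On the log scale, ln 24 = 3.18. With 60 evaluable subjects, 30 per sequence, one such subject moves the mean log ratio by 3.18/60 = 0.053, or about 5%. Subjects with the reverse pattern would offset this in the mean but add to the variance.

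**Effect on times.** Under the linear fit the shift is the same in both treatments, so T-R differences do not change. Ratios of short times change slightly: true onsets of 20 and 25 min (0.80) read as 17 and 22 (0.77).

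**The case against.** Several points against the concern are sound and limit it.

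- **The timing error is small.** It is 1-3 min on a 720-min clamp and nearly equal in both treatments. A reader might infer that all three endpoints are seriously wrong. The check does not support that, and tGIRlast is correct when infusion runs to 720 min.
- **The 24-fold ratio is a constructed case.** It needs an early stop at one visit, a full 12 h at the other, and equal true last rates. Protocol 4.2 cites typical clamp durations of 8 to 10 h for rapid-acting insulins and a half-life of 81 min, so many infusions may end early at both visits. The linear factor then cancels. A reader might take 24-fold as the expected error; nothing in the documents gives its frequency. Footnote b's cap at 720 min shows only that the SAP allows for clamps still infusing at that time.
- **The figures rest on choices the SAP leaves open.** That is fair for the sizes. It does not rescue the rule: both degrees give a wrong GIRlast after an early stop, and for a constant rate they differ about 7-fold (30% against 4.2%).
- **The 4.3.1 footnotes serve another purpose.** They set a window for clamp quality and do not define the endpoints. It would be too strong to call this a contradiction; it is two readings of start and end of GIR in one document.
- **A raw reading has its own weakness.** SAP 4.4 describes the minute data as strongly fluctuating, and an isolated late pulse could set both tGIRlast and GIRlast. Protocol 7.14.4 foresees intermittent infusion but deals with it only for clamp quality. This stands as a cost of the fix.

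**Conclusion.** The concern holds, chiefly for GIRlast. As written, GIRlast is about 4% of the real last rate (linear) or a variable fraction of it, 30% for a constant rate (quadratic), when infusion stops well before 12 h, and the full rate when infusion runs to 720 min. The T/R ratio is protected only under a linear fit with both clamps stopping by about 712 min. The shifts in tGIRonset and tGIRlast are real but minor.

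The direction follows from the SAP's own reading rule and 9-point neighbourhood. The sizes assume tricube weights and the stated profiles.

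A reader might go on to doubt the biosimilarity conclusion. The documents do not support that: GIRmax and AUC_GIR(0-12h) do not use these reading rules, and SAP 6.4.2.1 attaches the 80.00-125.00% requirement to the primary analyses. Only secondary endpoints are affected.

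**What to change.** In SAP 5.2.2 (3)-(5):

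- take tGIRonset as the Start of GIR in footnote a of 4.3.1;
- take tGIRlast as t_last, the last minute with recorded GIR above zero;
- take GIRlast as the recorded GIR at t_last.

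Name t_last itself, not the End of GIR in footnote b. After an early stop that End is t_last + 1, where recorded GIR is zero: last time would be 1 min late, and GIRlast would be zero with no logarithm for the model in 6.4.2.1.

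Keep the smoothed curve for GIRmax, tGIRmax, the 50% times and the AUCs. Integrate AUC_GIR(0-last) on the smoothed curve up to t_last. Under the linear fit and a constant last rate, the tail left out is worth 0.392 + 0.186 + 0.042 = 0.62 min at that rate, which is negligible. Amend the sentence in 5.2 that takes all PD parameters from smoothed data, and state the LOESS degree and weight function in 4.4.

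The cost is SAP wording only: the minute record exists, and its start and end are already derived for CV and DFT. The downside is that GIRlast becomes a single-minute reading open to an isolated late pulse. A stated positive threshold for a measurable GIR is an alternative.

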#### 6.4.2.2 Secondary Analysis

Similar analysis also will be performed on secondary PK/PD endpoints between Treatment T and R.

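### SAP Eqs. (27) and (28) end in − t_j where linear interpolation needs + t_j, so both half-maximal GIR times come out negative

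*SAP*

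**What the plan says.** SAP 5.2.2 (6) and (7) define tGIR50%E and tGIR50%L as the times at which the GIR curve stands at half its maximum, before and after the peak. The late one, for example, is "defined as the time reaching to 50% maximal GIR after" the time of GIRmax. Each "is obtained from the smoothed PD curve per interpolative rule".

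The equation printed for each has a fraction followed by a subtraction of t_j: "t_j - t_{j+1})}{GIR_j - GIR_{j+1}} - t_j". The right-hand side is identical in (27) and (28). Only the bracketing conditions differ: the early pair straddles half-maximum on the way up, the late pair on the way down.

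For the analysis, SAP 6.4.2.2 says only: "Similar analysis also will be performed on secondary PK/PD endpoints between Treatment T and R". The analysis it points back to, in 6.4.2.1, is an ANOVA on natural logarithms. The protocol synopsis, VI.4, plans T/R ratios of geometric means with 90% confidence intervals for secondary as well as primary endpoints. Neither document gives another formula for these two times.

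**The concern.** Interpolating between two adjacent points starts at the left-hand time and adds the fraction of the step needed to reach the target. Subtracting t_j instead gives a small positive number minus the left-hand time, which is a negative time after dosing.

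The two endpoints describe how fast insulin action rises and how long it lasts. If the SAP is programmed literally, they take impossible values and cannot enter a log-scale comparison. If a programmer silently corrects the sign, the reported analysis departs from the pre-specified formula. SAP 6.6.3 says the analysis programs are validated, but validation against this text would confirm the wrong formula.

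**Working it through.** **Inputs**
- Eqs. (27) and (28), SAP 5.2.2.
- Early bracket: GIR_j ≤ h < GIR_{j+1}, with t_j before the peak. Late bracket: GIR_j ≥ h > GIR_{j+1}, with t_j at or after the peak. Here h = GIRmax/2 (SAP 5.2.2).
- Time grid: "721 PD data points (0-720 min) were measured for each treatment" (SAP 4.4), so t_{j+1} − t_j = 1 min.
- Start of infusion: "the onset of insulin action was identified by a decline of 5mg/dL or more for glucose concentration from the baseline level" (SAP 4.3.1, footnote a); GIR starts at or after that point.

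The SAP gives no worked value for either endpoint, so there is no figure to reproduce.

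**Step 1: the fraction.** Write

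w = (h − GIR_j)(t_j − t_{j+1}) / (GIR_j − GIR_{j+1}) = (t_{j+1} − t_j) × (h − GIR_j)/(GIR_{j+1} − GIR_j).

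Under either bracket the last ratio lies in [0, 1). With a 1-min step, 0 ≤ w < 1 min.

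**Step 2: compare.** Linear interpolation gives t_j + w. The SAP prints w − t_j. Since w < 1, the printed result is below zero for every t_j ≥ 1 min.

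**Step 3: numbers** (GIR values assumed for illustration; GIRmax = 8, h = 4)

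| | Early, Eq. (27) | Late, Eq. (28) |
|---|---|---|
| Bracketing points | GIR(45) = 3.95, GIR(46) = 4.05 | GIR(240) = 4.05, GIR(241) = 3.95 |
| w | (4 − 3.95)(45 − 46)/(3.95 − 4.05) = 0.5 | (4 − 4.05)(240 − 241)/(4.05 − 3.95) = 0.5 |
| As printed | 0.5 − 45 = −44.5 min | 0.5 − 240 = −239.5 min |
| With + t_j | 0.5 + 45 = 45.5 min | 0.5 + 240 = 240.5 min |

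**Step 4: could the sign just be dropped?** |w − t_j| = t_j − w for t_j ≥ 1. The true time is t_j + w. The gap is 2w, which varies by subject and is always under 2 min. In the table it is 45.5 − 44.5 = 1.0 min.

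**Step 5: simulated curves.** In 5,000 smooth single-peaked curves on the 0–720 min grid (assumed onset 5–40 min, peak parameter 60–200 min), the printed formula was negative in 5,000 of 5,000 for each endpoint. With + t_j every value fell inside its bracket [t_j, t_{j+1}]. The absolute-value error averaged about 1.0 min, with a maximum just under 2.

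**Step 6: the planned analysis.** The logarithm of −44.5 or −239.5 is undefined, so no geometric mean ratio exists. An untransformed T − R comparison would also mislead. Writing t_T, t_R for the left-hand grid times, the printed formula gives (w_T − t_T) − (w_R − t_R) = −(t_T − t_R) + (w_T − w_R). Apart from the sub-minute term, the difference has the wrong sign.

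**The case against.** The strongest reply is that this is a typographical slip with little practical reach. The endpoints are fixed in words and by the bracketing conditions, a negative post-dose time shows itself on the first run, and programs are validated. Even someone who drops the minus sign errs by less than 2 min, with no evident reason for that error to differ between T and R. The equations concern two of the eleven secondary PD endpoints in SAP 2.4.3. All of this stands, and it limits the weight of the point. It does not make the printed rule usable: followed as written, it cannot return the quantity it defines.

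The log scale for these times is also partly an inference. SAP 6.4.2.2 promises a similar analysis, not the identical one, and 6.4.2.1 names logarithms only for the four primary endpoints. The firmer support is the protocol's plan for geometric mean ratios of secondary endpoints (synopsis VI.4).

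A misread sign in text taken from a PDF cannot be wholly excluded. However, the same minus appears in both equations, while plus signs in Eqs. (25), (26) and (29) are read correctly.

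A reader might go on to infer that every time endpoint needs a nonparametric analysis because times sit on a discrete grid. The documents do not support that here: the two half-maximal times are interpolated rather than grid values, positive times can be log-transformed, and nothing in the plan quantifies harm from ties. Nor does the sign error call for a rule on which crossing to use when a curve crosses half-maximum more than once. That is a separate question with more than one defensible answer.

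**Conclusion.** The formula is wrong as written in both equations. It returns w − t_j instead of t_j + w, which is negative for any realistic t_j, and the planned geometric mean ratios for tGIR50%E and tGIR50%L cannot be formed from it.

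It would be tempting to say that every value without exception is negative. Formally, t_j = 0 in Eq. (27) gives a value in [0, 1). That needs half-maximal GIR within the first minute after dosing, which does not fit an infusion that waits for glucose to fall by at least 5 mg/dL.

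It would also be tempting to read this as a threat to the biosimilarity conclusion. It is not: Cmax, AUC_IA(0–12h), GIRmax and AUC_GIR(0–12h) do not use Eq. (27) or (28). The effect stops at two secondary PD endpoints.

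The conclusion assumes the signs are as printed and the smoothed curve is evaluated each minute. SAP 6.1.1 admits PD subjects with some missing minutes (more than 90% of records required). If the curve is not evaluated at a missing minute, w is bounded by the width of that gap instead of 1 min, and the printed value is still negative whenever t_j is at least that width.

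**What to change.** In SAP 5.2.2, Eqs. (27) and (28), replace the final − t_j with + t_j, after checking both signs against the source document. Make the change before the PD programs are finalised and validated, so that the program and the pre-specified formula agree. The cost is two characters in the SAP, with no change to data collection, sample size or any primary analysis.

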### 5.2.3 Evaluation of PD Clamp Study for Net Insulin Aspart

In this clamp study, glucose infusion by controlled GIR neutralizes/offsets the effect of insulin to maintain euglycemia at the target level. However, both endogenous human insulin (HI) and exogenous insulin aspart (IA) are present in blood. To assess the contribution of net IA to the PD

profile, the PD GIR data should be adjusted by the IA fraction of total insulin (HI + IA). For a given subject  $i$  in Treatment  $X$  at time  $t$ , the IA fraction (denoted as  $f$ ) is defined as follows:

$$f_{IA}^{i,X}(t) = \frac{C_{IA}^{i,X}(t)}{C_{IA}^{i,X}(t) + C_{HI}^{i,X}(t)} \quad (29)$$

where  $t$  is the given time point for which PK data of both IA and HI are analyzed, and  $C$  is the concentration of corresponding insulins.

The smoothed GIR data are adjusted to the GIR that corresponding to the net IA by the calculation below:

$$G_{IA}^{i,X}(t) = G_{Smooth}^{i,X}(t) \times f_{IA}^{i,X}(t) \quad (30)$$

If the denominator of Eq. (29) = 0 for a time point  $t$ , then  $f(t) = 1$ , i.e., the GIR is not adjusted for the time point. The unadjusted PD data points will be tabulated.

The obtained  $G_{IA}(t)$  data are further used to calculate the  $G_{max}$  and  $AUC_{0-12hr}$  for the GIR corresponding to the net IA per Section 5.2.1. and further assess the 90% CI for T vs. R.

